7.2.2. Sensitivity and Supportive Analyses for Primary Endpoint

The primary endpoint will be analyzed with the PP population as a sensitivity analysis to the efficacy population.

7.3. Analysis of the Secondary Efficacy Parameter

Secondary efficacy analyses will be conducted for the efficacy evaluable population.

The proportion of participants who achieve response, defined as BOR of CR or PR, as determined by investigator assessment according to the response criteria listed in [Appendix A](#), will be estimated with its 95% CI.

The proportion of participants who achieve BOR of CCyR as assessed by local analysis and investigator evaluation will be estimated with its 95% CI.

The proportion of participants who achieve BOR of PCyR as assessed by local analysis and investigator evaluation will be estimated with its 95% CI.

Duration of CR is defined as the time from first assessment of CR to the earlier of disease progression or death due to any cause. Participants without disease progression or death at the time of analysis will be censored at the date of last response assessment before the cutoff date. Participants who start a new cancer therapy or have stem cell transplant before disease progression will be censored at the date of last response assessment before new cancer therapy start or transplant. Duration of CR will be analyzed by the Kaplan-Meier method. The Kaplan-Meier estimate of median duration of CR will be presented with its 95% CI. The 95% CI will be calculated using the Brookmeyer and Crowley's method ([Brookmeyer and Crowley 1982](#)).

Duration of response is defined as the time from first assessment of CR or PR to the earlier of disease progression or death due to any cause. Participants without disease progression or death at the time of analysis will be censored at the date of last response assessment before the cutoff

date. Participants who start a new cancer therapy or have stem cell transplant before disease progression will be censored at the date of last response assessment before new cancer therapy start or transplant. Duration of response will be analyzed by the Kaplan-Meier method. The 95% CI will be calculated using the Brookmeyer and Crowley's method ([Brookmeyer and Crowley 1982](#)).

Progression-free survival is defined as the time from the first date of taking study drug until the date of disease progression, as measured by response criteria or until death due to any cause, whichever is earlier. Participants who are still alive without experiencing disease progression at the time of analysis will be censored at the date of the last response assessment before the cutoff date. Participants who start a new cancer therapy or have stem cell transplant before disease progression will be censored at the date of last response assessment before new cancer therapy start or transplant. Progression-free survival data will be analyzed by the Kaplan-Meier method. The 95% CI will be calculated using the Brookmeyer and Crowley's method ([Brookmeyer and Crowley 1982](#)).

Overall survival is defined as the time from the first day of taking study drug until death due to any cause. Participants without death observed at the time of the analysis will be censored at last date known to be alive. Overall survival will be analyzed by the Kaplan-Meier method. The 95% CI will be calculated using the Brookmeyer and Crowley's method ([Brookmeyer and Crowley 1982](#)).

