2.2.2. Secondary Endpoints

The secondary endpoints for this study are as follows:

- The proportion of subjects who achieve response, defined as a best response of CR or PR, as determined by investigator assessment according to the response criteria listed in [Appendix E](#).
- The proportion of subjects who achieve a complete cytogenetic response (CCyR) as assessed by local analysis and investigator evaluation.
- The proportion of subjects who achieve a partial cytogenetic response (PCyR) as assessed by local analysis and investigator evaluation.
- Duration of CR, defined as the time from first assessment of CR to the earlier of disease progression or death due to any cause.

- Duration of response, defined as the time from first assessment of CR or PR to the earlier of disease progression or death due to any cause.
- Progression-free survival.
- Overall survival.
- Safety and tolerability, as assessed by evaluating the frequency, duration, and severity of AEs; through review of findings of physical examinations, changes in vital signs, and electrocardiograms (ECGs); and through clinical laboratory blood and urine sample evaluations.

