APPENDIX E. RESPONSE CRITERIA FOR MYELOID/LYMPHOID NEOPLASMS WITH FGFR1 REARRANGEMENT

Table E1: Response Criteria

Response Subcategory	Response Criteria
CR ^a	
Presence of all of the following improvements:
 
 1. Bone marrow: $\leq 5\%$ myeloblasts (including monocytic blast equivalent) and no lymphoblasts, with normal maturation of all cell lines, and return to normal cellularity^b. 2. Osteomyelofibrosis absent or equal to "mild reticulin fibrosis" (Grade 1 or less fibrosis)^c 3. Peripheral blood^d 
 - WBC $\leq 10 \times 10^9$ cells/L. - Hgb ≥ 11 g/dL. - Platelets $\geq 100 \times 10^9/L; \leq 450 \times 10^9/L$. - Neutrophils $\geq 1.0 \times 10^9/L$. - Blasts = 0%. - Neutrophil precursors reduced to $\leq 2\%$. - Monocytes $\leq 1 \times 10^9/L$. - Eosinophils $\leq 0.5 \times 10^9/L$. 4. Extramedullary disease: Complete resolution of extramedullary disease present before therapy (eg, lymphadenopathy), including palpable hepatosplenomegaly. 
NOTE: Persistent low-level dysplasia is permitted given subjectivity of assignment of dysplasia^b.

PR	
Presence of all of the following improvements:
 
 1. Reduction of bone marrow blasts (and blast equivalents) by 50%, but remaining $> 5\%$ of cellularity (except in cases with $\leq 5\%$ bone marrow blasts at baseline). 2. Normalization of peripheral blood indices listed in CR Criterion 3. 3. Extra medullary disease response of CMR/CR or PMR/PR (see Table E2).
Progression of disease	
Combination of 2 major criteria, 1 major and 2 minor criteria, or 3 minor criteria from following lists:
 
Major criteria:
 
 • Increase in blast counta 
 ○ $< 5\%$ blasts: $\geq 50\%$ increase and to $> 5\%$ blasts. ○ 5%-10% blasts: $\geq 50\%$ increase and to $> 10\%$ blasts. ○ 10%-20% blasts: $\geq 50\%$ increase and to $> 20\%$ blasts. ○ 20%-30% blasts: $\geq 50\%$ increase and to $> 30\%$ blasts. • Evidence of cytogenetic evolution 
 ○ Re-appearance of a previously present or appearance of a new cytogenetic abnormality in complete cytogenetic remission via classic karyotyping or FISH. ○ Increase in cytogenetic burden of disease in partial cytogenetic remission by $\geq 50\%$ via classic karyotyping or by $\geq 50\%$ and involving at least 10% (eg, 2/200) of cells via FISH.

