Table E1: Response Criteria (Continued)

Response Subcategory	Response Criteria
Progression of disease (continued)	
 • New or worsening extramedullary disease 
 ○ Worsening splenomegaly 
 ▪ Progressive splenomegaly that is defined by IWG-MRT: the appearance of a previously absent splenomegaly that is palpable at > 5 cm below the left costal margin or a minimum 100% increase in palpable distance for baseline splenomegaly of 5 to 10 cm or a minimum 50% increase in palpable distance for baseline splenomegaly of > 10 cm. ○ Extramedullary disease outside of the spleen. 
Minor criteria:
 
 • Transfusion dependence.^e • Significant loss of maximal response on cytopenias $\geq 50\%$ decrement from maximum remission/response in granulocytes or platelets. • Reduction in Hgb by $\geq 1.5\text{ g/dL}$ from best response or from baseline as noted on complete blood count. • Evidence of clonal evolution (molecular).
Stable disease	
Meeting neither progression of disease nor response criteria.
 
Subjects with stable disease will be further characterized according to criteria presented in Table E3.

Cytogenetic Response^f	
Complete (cCyR)	0% 8p11 translocated metaphases as seen on classic karyotyping with minimal of 20 metaphases, or FISH.
Partial (pCyR)	Decrease from baseline of 50% or more 8p11 translocated metaphases as seen on classic karyotyping with minimal of 20 metaphases, or FISH.

CR = complete response; FISH = fluorescence in situ hybridization; Hgb = hemoglobin; IWG-MRT = International Working Group-Myeloproliferative Neoplasms Research and Treatment; PR = partial response; WBC = white blood cell.

^a Given the current lack of a validated tool to assess complete resolution of symptoms, "CR with resolution of symptoms" (a complete resolution of disease-related symptoms as noted by the MPN-SAF in presence of CR) will be a provisional category of disease response.

^b Presence of dysplastic changes, which may be interpreted within the scope of normal range of dysplastic changes, may still exist in the presence of CR as allowed in MDS IWG. Marrow should exhibit age-adjusted normocellularity in CR.

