APPENDIX A. RESPONSE CRITERIA FOR MYELOID/LYMPHOID NEOPLASMS WITH FGFR1 REARRANGEMENT

Table A1: Response Criteria

Response Subcategory	Response Criteria
CR ^a	
Presence of all of the following improvements:
 
 1. Bone marrow: $\leq 5\%$ myeloblasts (including monocytic blast equivalent) and no lymphoblasts, with normal maturation of all cell lines, and return to normal cellularity^b. 2. Osteomyelofibrosis absent or equal to “mild reticulin fibrosis” (Grade 1 or less fibrosis)^c 3. Peripheral blood^d 
 – WBC $\leq 10 \times 10^9$ cells/L. – Hgb ≥ 11 g/dL. – Platelets $\geq 100 \times 10^9/L; \leq 450 \times 10^9/L$. – Neutrophils $\geq 1.0 \times 10^9/L$. – Blasts = 0%. – Neutrophil precursors reduced to $\leq 2\%$. – Monocytes $\leq 1 \times 10^9/L$. – Eosinophils $\leq 0.5 \times 10^9/L$. 4. Extramedullary disease: Complete resolution of extramedullary disease present before therapy (eg, lymphadenopathy), including palpable hepatosplenomegaly. 
NOTE: Persistent low-level dysplasia is permitted given subjectivity of assignment of dysplasia^b.

PR	
Presence of all of the following improvements:
 
 1. Reduction of bone marrow blasts (and blast equivalents) by 50%, but remaining $> 5\%$ of cellularity (except in cases with $\leq 5\%$ bone marrow blasts at baseline). 2. Normalization of peripheral blood indices listed in CR Criterion 3. 3. Extra medullary disease response of CMR/CR or PMR/PR (see Table D2).
Progression of disease	
Combination of 2 major criteria, 1 major and 2 minor criteria, or 3 minor criteria from following lists:
 
Major criteria:
 
 • Increase in blast count^a 
 ○ < 5% blasts: $\geq 50\%$ increase and to $> 5\%$ blasts. ○ 5%-10% blasts: $\geq 50\%$ increase and to $> 10\%$ blasts. ○ 10%-20% blasts: $\geq 50\%$ increase and to $> 20\%$ blasts. ○ 20%-30% blasts: $\geq 50\%$ increase and to $> 30\%$ blasts. • Evidence of cytogenetic evolution 
 ○ Re-appearance of a previously present or appearance of a new cytogenetic abnormality in complete cytogenetic remission via classic karyotyping or FISH. ○ Increase in cytogenetic burden of disease in partial cytogenetic remission by $\geq 50\%$ via classic karyotyping or by $\geq 50\%$ and involving at least 10% (eg, 2/200) of cells via FISH.

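### Duration of CR counts only protocol-defined progression or death, so loss of CR below the progression threshold is never an event and the endpoint will tend to overstate how long CR lasts.

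*SAP*

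**What the plan says.** Protocol 2.2.2 lists "Duration of CR, defined as the time from first assessment of CR to the earlier of disease progression or death due to any cause". Protocol 9.4.1.2 and SAP Table 1 use the same start and the same two events. SAP 7.3 does too: "Duration of CR is defined as the time from first assessment of CR to the earlier of disease progression or death", whatever the cause of death.

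For subjects without an event, the SAP rule is: "Participants without disease progression or death at the time of analysis will be censored at the date of last response assessment before the cutoff". Response status at that assessment plays no part. The SAP adds a rule that Protocol 9.4.1.2 does not have: "Participants who start a new cancer therapy or have stem cell transplant before disease progression will be censored at the date of last response assessment", that is, the last one preceding the new treatment.

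Progression is defined in Protocol Appendix E, Table E1 (repeated in SAP Appendix A, Table A1) as "Combination of 2 major criteria, 1 major and 2 minor criteria, or 3 minor criteria from following lists". Stable disease is "Meeting neither progression of disease nor response criteria". CR requires all of its marrow, fibrosis, blood and extramedullary items together.

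SAP 7.4 repeats duration of CR under central review and gives no different event definition. Protocol 6.4.2 lets disease status follow-up end at progression or relapse, but relapse is not defined in the response criteria and is not an event in SAP 7.3.

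**The concern.** CR is lost when any one of its items fails. Progression needs a combination of findings. Between the two lies a region where a subject is no longer in CR, has not progressed, and has no event.

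The primary endpoint is a best response of CR, so it says nothing about how long CR lasted. Duration of CR is the endpoint that readers will use for that. As defined, it measures time from first CR to multi-criterion progression or death. It shares its events and censoring with duration of response and differs only in its start date, so it cannot register a change from CR to PR, or from CR to stable disease.

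**Working it through.** The plan gives no assumed or target duration of CR, so there is no figure to reproduce. The check is a comparison of the definitions, followed by the exam intervals and an illustration on assumed inputs.

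**Step 1: combinations short of progression.** Table E1 has 3 major criteria (blasts, cytogenetic evolution, extramedullary disease) and 4 minor ones. Applying the rule to every count leaves four non-empty combinations that are not progression: 1 major + 0 minor, 1 major + 1 minor, 0 major + 1 minor, and 0 major + 2 minor.

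**Step 2: cases in that region that fail CR.**

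| Case | Progression count | CR item failed | Event? |
|---|---|---|---|
| Resolved extramedullary disease outside the spleen recurs alone | 1 major | Item 4 (complete resolution) | No |
| Marrow blasts rise from 2% to 25%, in a subject not in cytogenetic remission or without reappearance of the 8p11 abnormality | 1 major | Item 1 (at most 5%) | No |
| The same, with a hemoglobin fall of at least 1.5 g/dL | 1 major + 1 minor | Item 1 | No |
| Transfusion dependence (hemoglobin below 8.5 g/dL) with a hemoglobin fall of at least 1.5 g/dL | 2 minor | Item 3 (at least 11 g/dL) | No |

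The condition in the second row matters. The cytogenetic criterion is written for subjects in complete or partial cytogenetic remission, and CR has no cytogenetic item. A subject can therefore be in CR with only "Increase in blast count" available as a major criterion.

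**Step 3: what the SAP then does.** A subject in any of these rows contributes event-free time until later progression or death, or is censored at the last response assessment. If new therapy or transplant follows, the subject is censored before it. In none of these routes is the loss of CR an event. Where the new treatment was given because CR was lost, the censoring is likely to be informative.

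**Step 4: possible lag.** Protocol Table 7 sets marrow exams every 9 weeks in the first 12 months, after the first exam at 6 weeks. After that they are every 18 weeks without CCyR, or every 52 weeks with confirmed CCyR. If loss of CR precedes progression by one scheduled exam in a subject without CCyR, the excess is about 9 weeks in year 1 and 18 weeks later.

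**Step 5: illustration, all inputs assumed.** Let time to loss of CR be exponential with median m. A share f of subjects lose CR first and progress after an exponential lag with median L; the rest lose CR at progression. There is no censoring. With a = ln 2/m and b = ln 2/L (b ≠ a):

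S(t) = (1 − f)e^(−at) + f(b·e^(−at) − a·e^(−bt))/(b − a)

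When a = b, the second term is f(1 + at)e^(−at). The median under the SAP definition solves S(t) = 0.5. For m = 12, f = 0.5, L = 6 and t = 16.7 months: e^(−at) = 0.382, e^(−bt) = 0.146, and 0.5 × 0.382 + 0.5 × (2 × 0.382 − 0.146) = 0.500.

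| Median time to loss of CR (months) | f = 25%, L = 3 | f = 100%, L = 12 |
|---|---|---|
| 6 | 7.1 | 21.3 |
| 12 | 13.3 | 29.1 |
| 24 | 25.2 | 42.5 |

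The right-hand column is a deliberate extreme. The width of the range shows that the effect could be slight or large, and the documents do not say which.

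**The case against.** Progression or death is a prespecified event definition, identical in both documents, and it is defensible for duration of response. The endpoint is secondary, and SAP 7.1 states no hypotheses. Response, marrow, lesion and transfusion data are listed by subject (SAP Appendix C), so a reader of the listings could trace loss of CR. All of this stands, and it limits the consequence. It does not make the label match the quantity.

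Four stronger readings are tempting, and the documents do not support them.

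- **The endpoint can only overstate.** A subject can progress with every CR item intact. Suppose hemoglobin falls from 14 to 12 g/dL, platelets fall from 400 to 190 × 10^9/L ((400 − 190)/400 = 52.5%), and molecular clonal evolution appears. That is 3 minor criteria, and the duration ends while the CR criteria are still met. The SAP time is never the shorter one only when compared with a composite that also counts progression.
- **Any blast relapse is missed.** Cytogenetics are assessed on the marrow aspirate. In a subject in CCyR, a blast increase with reappearance of the 8p11 abnormality is 2 major criteria and therefore progression.
- **The lag may be 52 weeks.** That interval applies only to confirmed CCyR, so CR would have to be lost while CCyR is kept. Table 7 also calls for an unscheduled marrow when blood suggests progression, and hematology is scheduled each cycle.
- **The subject is still classified as in CR.** Nothing in the SAP does this. The subject's category changes, but no event is recorded.

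The central review charter is not among the documents, so how that committee handles relapse is unknown.

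**Conclusion.** The definition does not measure how long CR lasts. It measures time from first CR to multi-criterion progression or death, and loss of CR below the threshold is either carried as event-free time or censored. The expected direction is overstatement, as a tendency rather than a certainty for each subject.

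The number of subjects affected and the shift in the median cannot be derived from the documents. The 9-week and 18-week figures assume a lag of exactly one scheduled marrow exam in a subject without CCyR, and they shrink if an unscheduled marrow is done. The medians in the illustration rest wholly on assumed rates and lags. The primary CR rate uses best response and is untouched. The point is worth acting on because this endpoint carries the durability claim for the primary result and the data needed are already recorded.

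**What to change.** In SAP 7.3, describe the present endpoint as time from first CR to progression or death. Add a supplementary Kaplan-Meier analysis of duration of CR, by investigator and by central review, whose event is the first of:

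- documented loss of CR, meaning marrow or extramedullary disease failing the CR criteria, or blood counts failing CR Criterion 3 on at least 2 analyses over at least 8 weeks, excluding cytopenias attributed to therapy;
- progression;
- death.

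The 8-week rule mirrors footnote d of Table E1, and the cytopenia exclusion mirrors footnote e. Without them, short-lived or drug-related count changes would be counted as loss of CR. The SAP should also say which failing blood analysis dates the loss, and whether relapse in Protocol 6.4.2 means the same thing. Report the two analyses side by side. Label the new one supplementary: the SAP is dated 24 FEB 2021, and Protocol 1.3.2 reports 47 treated participants as of 16 APR 2023.

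The cost is one extra derived endpoint from data already collected and listed, a possibly shorter reported duration, and some remaining misclassification of transient count changes. No primary analysis or clinical rule changes.

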6.4.2.1. Post-Transplant Follow-Up

Subjects who have a successful HSCT should be followed for disease status post-transplant as well. Data from standard-of-care transplant assessments (eg, pretransplant preparation, conditioning regimen, donor, type, GVHD, relapse, transplant-related mortality, graft failure, peripheral blood smears, CBCs, differentials, bone marrow biopsy, bone marrow aspirate, cytogenetics) will be collected from these subjects until they have withdrawn from the study.

Post-transplant subjects should return to the investigative site for bone marrow exams, hematology blood work and, if applicable, imaging studies, as noted in Section [7.6](#).

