9.4.1.2. Secondary Efficacy Analyses

Secondary efficacy analyses will be conducted for the efficacy evaluable population.

The proportion of subjects who achieve response, defined as BOR of CR or PR, as determined by investigator assessment according to the response criteria listed in [Appendix E](#), will be estimated with its 95% CI.

The proportion of subjects who achieve BOR of CCyR as assessed by local analysis and investigator evaluation will be estimated with its 95% CI.

The proportion of subjects who achieve BOR of PCyR as assessed by local analysis and investigator evaluation will be estimated with its 95% confidence interval.

Duration of CR, defined as the time from first assessment of CR to the earlier of disease progression or death due to any cause. Subjects without disease progression or death at the time of analysis will be censored at the date of last response assessment before the cutoff date.

Duration of CR will be analyzed by the Kaplan-Meier method.

Duration of response, defined as the time from first assessment of CR or PR to the earlier of disease progression or death due to any cause. Subjects without disease progression or death at the time of analysis will be censored at the date of last response assessment before the cutoff date. Duration of response will be analyzed by the Kaplan-Meier method.

Progression-free survival is defined as the time from the first date of taking study drug until the date of disease progression, as measured by response criteria or until death due to any cause, whichever is earlier. Subjects who are still alive without experiencing disease progression at the time of analysis will be censored at the date of the last response assessment before the cut-off date. Progression-free survival data will be analyzed by the Kaplan-Meier method.

Overall survival is defined as the time from the first day of taking study drug until death due to any cause. Subjects without death observed at the time of the analysis will be censored at last date known to be alive. Overall survival will be analyzed by the Kaplan-Meier method.

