9.1. Changes to Protocol-Defined Analyses

Efficacy evaluable population is updated to only include participants with FGFR1 rearrangement and with at least 1 prior systemic therapy per health authority request.

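### The SAP censors PFS, duration of CR and duration of response at transplant or new therapy; the Protocol does not, the change is not logged, and no analysis under the Protocol rule is planned

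*SAP*

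**What the plan says.** Protocol 9.4.1.2 defines PFS as running to progression, "as measured by response criteria or until death due to any cause, whichever is earlier". Its only censoring rule for PFS is: "Subjects who are still alive without experiencing disease progression at the time of analysis will be censored at the date of the last response assessment" preceding the cutoff. For duration of CR and duration of response the parallel rule is: "Subjects without disease progression or death at the time of analysis will be censored at the date of last response assessment before the cutoff date". Neither transplant nor new therapy is mentioned.

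SAP 7.3 keeps the same event definitions and the same cutoff rule. For each of the three endpoints it then adds: "Participants who start a new cancer therapy or have stem cell transplant before disease progression will be censored at the date of last response assessment" (the one preceding the new therapy or the transplant).

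Protocol 6.4.2.1 states: "Subjects who have a successful HSCT should be followed for disease status post-transplant as well". It collects relapse and transplant-related mortality, and Protocol Table 7 sets marrow examinations at 1 to 3 months and at 6 months after transplant.

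The only entry in SAP 9.1 concerns the analysis population: "Efficacy evaluable population is updated to only include participants with FGFR1 rearrangement" and with prior systemic therapy. The only analysis that the SAP labels as a sensitivity analysis (SAP 7.2.2) is the per-protocol analysis of the primary endpoint.

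**The concern.** Kaplan-Meier estimation treats a censored subject as having the same later risk as those still being followed. Transplant and a change of therapy are decisions that may depend on how the disease is going, so that assumption cannot be taken for granted here. The added rule also changes what is estimated. The Protocol version describes time to progression or death whatever treatment follows. The SAP version describes that time as if transplant and new therapy did not occur.

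The trial is small. At the planned 46 subjects and the assumed 35% CR rate, about 0.35 × 46 = 16 subjects enter the duration-of-CR analysis, so a handful of transplants can move it. Someone reading the results against the Protocol would assume that post-transplant relapses and deaths are included. Nothing in the SAP's list of changes says otherwise, and no second estimate is planned to show how much the rule matters.

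**Working it through.** The plan gives no design figure for PFS or for either duration, so there is none to reproduce. Its one probability statement concerns the CR rate, which this rule does not touch.

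**1. How each document treats the same subject**

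| Course | Protocol 9.4.1.2 | SAP 7.3 |
|---|---|---|
| Progression or death with no earlier transplant or new therapy | event | event |
| Transplant before progression, later relapse or death | event | censored at last assessment before transplant |
| Other new therapy before progression, later death | event | censored at last assessment before the therapy |
| New therapy or transplant only after progression | event (at progression) | event (at progression) |
| No event, transplant or new therapy by cutoff | censored at last assessment | censored at last assessment |

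The documents part in the second and third rows. The departure is an added censoring rule, not a different event definition.

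**2. Is the change logged, or offset by another analysis?**

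- SAP 9.1 has one entry, on the population.
- SAP 7.4 repeats the endpoints by central review. That changes the assessor and states no other censoring rule.
- The transplant summary in SAP 7.4 does not re-estimate PFS or duration.
- Appendix C lists one table each for duration of CR, duration of response and PFS (2.2.1, 2.2.2, 2.2.4). Parts of SAP 7.5 are redacted, but that section is exploratory.
- The SAP cites Protocol Amendment 5; the Protocol in hand is Amendment 6. The itemized Amendment 6 changes include none to Section 9.4.1.2. Unitemized administrative edits cannot be excluded.

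**3. Duration of CR, a count example**

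From the documents: 46 subjects and a 35% CR rate, so N = 16. Assumed: k = 5 transplanted at 6 months after CR, d = 4 events at 9 months among the other 11, none earlier, and j of the 5 with an event by 12 months.

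- SAP rule: 1 − d/(N − k) = 1 − 4/11 = 63.6%. Any censoring date before month 9 gives the same risk set of 11.
- Protocol rule: 1 − (d + j)/N.
  - j = 0: 1 − 4/16 = 75.0%
  - j = 2: 1 − 6/16 = 62.5%
  - j = 4: 1 − 8/16 = 50.0%

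The two rules agree when j/k = d/(N − k), that is j = 5 × 4/11 = 1.8. With fewer events among the transplanted the SAP rule gives the lower estimate; with more it gives the higher one.

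**4. PFS at 12 months, a constant-risk example**

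All inputs are assumed: exponential PFS with an 18-month median absent transplant; a share p of those event-free at 6 months is transplanted then; a share e of these has an event in the next 6 months. Censoring is taken at the transplant date for simplicity.

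- Event-free at 6 months: S6 = 0.5^(6/18) = 79.4%, so the background event share over any 6 months is 20.6%.
- SAP rule: S6 × S6 = 63.0%.
- Protocol rule: S6 × [(1 − p) × S6 + p × (1 − e)].

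| | e = 5% | e = 10% | e = 20% | e = 40% |
|---|---|---|---|---|
| p = 20% | 65.5% | 64.7% | 63.1% | 59.9% |
| p = 35% | 67.3% | 65.9% | 63.2% | 57.6% |

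The difference vanishes when e is close to the background 20.6% and changes sign on either side of it.

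**The case against.** The strongest reply is that this is a choice of estimand, and a legitimate one. The estimates are secondary, descriptive and from a single arm: SAP 7.1 marks hypotheses as not applicable, and Protocol 4.2 plans no comparisons. That stands, and it is why the rule need not be dropped. It does not explain why the change is missing from SAP 9.1.

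A second reply also stands in part. For non-transplant therapy the rule fits the data collection. Protocol 6.4.2 lists the start of new antineoplastic therapy as a point where disease-status follow-up stops, and survival follow-up continues. Protocol 7.10.1 mentions tumor assessments from records, but scheduled assessment has ended. The departure is therefore clearest for transplant, where continued disease assessment is specified.

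Two stronger readings are tempting, and the documents support neither.

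- A reader might infer that the rule flatters PFS and durability. The documents give no transplant rate, no post-transplant risk and no expected PFS, and both examples above move either way. A post-transplant event share that sounds high can still be no more than background: 20% over 6 months changes almost nothing in the second example.
- A reader might infer that post-transplant events are lost altogether. Later deaths count in full in overall survival, which has no such censoring. SAP 7.4 lists transplant outcomes, including transplant-related mortality, and summarizes them if numbers suffice (eg, more than 10 participants). Switches after progression are unaffected.

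**Conclusion.** The point holds as a discrepancy between the documents. SAP 7.3 overrides the Protocol's censoring rule for three secondary endpoints, SAP 9.1 does not record it, and no planned analysis shows the result under the Protocol rule. The textual finding rests on Section 9.4.1.2 being unchanged between Amendments 5 and 6, which the itemized changes support.

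The censoring may be informative. Neither the size nor the direction of its effect can be derived from the documents. On the assumed counts, the 12-month duration-of-CR estimate under the Protocol rule lies between 11.4 points above (75.0 − 63.6) and 13.6 points below (63.6 − 50.0) the SAP figure. This shows how sensitive a group of about 16 responders could be; it is not a forecast. The CR rate and overall survival are unaffected, so this is a correction worth making rather than a threat to the primary result.

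**What to change.** - Record the censoring rule in SAP 9.1 as a change from Protocol 9.4.1.2, with its reason. The rule may remain the main analysis.
- Add one sensitivity analysis of PFS, duration of CR and duration of response under the Protocol rule, chiefly without censoring at transplant, and list the tables in Appendix C.
- In both analyses, report the number censored for each reason: transplant, other new therapy, and no event at cutoff.

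The cost is one log entry and a few more Kaplan-Meier tables. For transplanted subjects the Protocol already requires the data. The limitation to state with the tables is that, after a non-transplant new therapy, the uncensored analysis will rest mainly on deaths.
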